6. ADVERSE EVENTS

Given the observational design of this study, there is no anticipated risk of adverse events associated with study participation.

6.1 DEFINITIONS

Adverse Event (AE): any untoward medical occurrence in a patient or clinical study subject.

Serious Adverse Event (SAE): any untoward and unexpected medical occurrence or effect that:

- Results in death
- Is life-threatening – refers to an event in which the subject was at risk of death at the time of the event; it does not refer to an event which hypothetically might have caused death if it were more severe
- Requires hospitalisation, or prolongation of a current inpatient's hospitalisation
- Results in persistent or significant disability or incapacity
- Is a congenital anomaly or birth defect

Medical judgement should be exercised in deciding whether an AE is serious in other situations, or performed by a delegated person according to the study delegation log. Important AEs that are not immediately life-threatening or do not result in death or hospitalisation (but may jeopardise the subject or require intervention to prevent one of the other outcomes listed in the definition above), should also be considered serious.

6.2 REPORTING PROCEDURES

All adverse events will be recorded during hospitalisation using the case report form. Babies who suffer hypoxic ischaemic encephalopathy are expected to have higher mortality and morbidity up to two years of age.

All serious adverse events that are not expected to occur in babies with hypoxic ischaemic encephalopathy (systemic venous thrombosis, massive intracranial bleeds), should be reported to the Chief Investigator by completing an SAE form and sending it within 24h. Please send any SAE forms to: [contact], [contact]

The Chief Investigator must notify the Sponsor of all unexpected SAEs. If there was any unexpected SAE which would be considered study related, the Chief Investigator will report to the Ethics Committee within 15 days of becoming aware of the event, using the SAE form. Local investigators should report any SAEs as required by their Sponsor and/or Research & Development Office.

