4.6 Sample collection and processing

All samples should be collected in pre-assembled sample collection packs containing a PAXgene bottle (for gene expression) and 2 EDTA bottles (for epigenetics and CNVs) with printed barcodes. The sample collection packs will be provided to all recruiting centres.

Genomic Imaging in Neonatal Encephalopathy

A total of approximately half a teaspoon (3 ml) of blood will be collected by venepuncture during blood sampling for routine clinical care or via indwelling arterial catheter, into 2 EDTA bottles and 1 PAXgene bottle by local clinicians/nurses, within 6 hours of birth from all recruited babies. In addition, 5ml of blood will be collected by venepuncture from each parent into EDTA bottles by local clinicians/nurses/phlebotomists or research nurses, wherever possible. This will allow us to examine the proportion of CNVs that are genetically transmitted in comparison to de novo mutations. The collected blood samples will be labelled using pre-printed barcodes (anonymised using the study number and date/time of collection) and will be transported to Imperial College London for analysis in batches.

Details of antenatal and postnatal events, and other routine clinical and imaging data will be collected. We will also obtain relevant clinical data from the participants' (baby and mother) medical records or from GPs/local hospitals if needed (GPs will be informed of study participation unless otherwise requested by parents). We will also collect the 3 Tesla MR data that is acquired as a part of routine clinical care. Parents will be contacted regularly via their preferred method of contact. Study newsletters will be sent to parents, unless they opt out.

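### SAE reporting filters on expectedness in the disease before relatedness, so a serious sampling-related event of a kind common in HIE requires no central SAE report

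*Protocol*

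**What the plan says.** Protocol section 6.1 defines an SAE as "any untoward and unexpected medical occurrence or effect that" meets one of the listed outcomes, of which death is the first. It does not say against what reference expectedness is judged. A closing paragraph lets medical judgement class other important events as serious and does not repeat the expectedness condition.

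Section 6.2 then sets out the reporting path:

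- Every adverse event during the hospital stay goes on the case report form.
- The background is described in general terms: "Babies who suffer hypoxic ischaemic encephalopathy are expected to have higher mortality and morbidity up to two years of age". There is no list of expected events.
- An SAE form is due to the Chief Investigator within 24 hours for "All serious adverse events that are not expected to occur in babies with hypoxic ischaemic encephalopathy (systemic venous thrombosis, massive intracranial bleeds"; the bracket closes after these two examples.
- Next, "The Chief Investigator must notify the Sponsor of all unexpected SAEs".
- Last, "If there was any unexpected SAE which would be considered study related, the Chief Investigator will report to the Ethics Committee", within 15 days.
- Separately, local investigators report SAEs as their own Sponsor or R&D office requires.

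The study procedure itself is in section 4.6. About 3 ml of blood is taken from the baby within 6 hours of birth, by venepuncture alongside routine sampling or through an arterial catheter already in place. For the parents, "In addition, 5ml of blood will be collected by venepuncture from each parent into EDTA bottles", where possible.

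**The concern.** Seriousness, expectedness and relatedness are three separate judgements. Here expectedness is folded into seriousness in 6.1 and applied again in 6.2. Relatedness comes last and only among the events that remain. Expectedness is also measured against the disease, whereas the only physical procedure the study adds is blood sampling.

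The reports that reach the Chief Investigator are therefore selected by how unusual an event is in HIE, not by whether the study may have caused it. Section 6 starts from the premise that participation carries no foreseeable risk, and section 4.5 says much the same for the baby. A safety rule in such a study should at least be able to contradict that premise. Because blood may be taken from the baby before the parents have consented (section 7.2), a clear route for any harm from sampling is worth having even if such harm is rare.

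**Working it through.** No figure in the protocol bears on this, so the check is a trace of the reporting path and a comparison of the two sections.

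**Trace.** Take two serious events in a baby during the hospital stay. Event A is attributed by the site to the research blood draw but is of a kind common in HIE. Event B is a systemic venous thrombosis unrelated to the study.

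| Step (Protocol) | Condition | Event A | Event B |
|---|---|---|---|
| Case report form (6.2) | any adverse event in hospital | recorded | recorded |
| SAE definition (6.1) | listed outcome, and unexpected | not met if judged against HIE | met |
| Form to Chief Investigator, 24 hours (6.2) | SAE not expected in HIE | not required | required |
| Notice to Sponsor (6.2) | unexpected SAE | not required | required |
| Ethics Committee, 15 days (6.2) | unexpected and study related | not required, although related | not required, because unrelated |
| Local report (6.2) | as Sponsor or R&D office requires | possible | possible |

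Event A is the one the study may have caused, and no central step requires it to be reported. Event B, which the study did not cause, must be sent within 24 hours. For event B this takes the bracketed examples as instances of events not expected in HIE, which is the natural reading of the sentence.

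The relatedness condition appears in one row only. By then event A has already dropped out, and no step before it asks the site to judge causality.

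**Width of the filter.** The only description of what is expected is raised mortality and morbidity up to two years. With no list, a site can place most serious events in these babies inside the expected set.

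**Consistency of 6.1 with 6.2.** There are two possibilities:

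1. Every SAE is unexpected by definition, as 6.1 says. Then the expectedness qualifiers at the Chief Investigator, Sponsor and Ethics Committee steps in 6.2 are redundant.
2. Expected SAEs exist, as the qualifiers in 6.2 imply. Then the definition in 6.1 is too narrow.

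The two could be reconciled only if unexpected had a different meaning in each section, and the protocol gives no such distinction. A death from HIE shows the problem. It meets the first listed outcome in 6.1, yet 6.2 describes raised mortality as expected. One site could call it an SAE that needs no expedited report, and another could say that it is not an SAE.

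**The case against.** A reader might infer that such events never come to the attention of the Chief Investigator, Sponsor or Ethics Committee, or that the rule would detect almost no harm from sampling. The protocol does not support that. All in-hospital adverse events are recorded on the case report form without any filter. A sample taken within 6 hours of birth would normally show an acute harm during that stay. The local-reporting sentence leaves a conditional route to a Sponsor or R&D office, and the last paragraph of 6.1 gives investigators discretion over seriousness. A site that blames a deterioration on a blood draw might also reasonably call it unexpected, and nothing forbids that. Nor is every bleed filtered out, since massive intracranial bleeds are among the bracketed events.

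A reader might also count the 600 planned parents as a gap, because expectedness is framed only for babies with HIE. That shows no lost reports. A serious event in a parent is not one expected in babies with HIE, so the filter does not remove it.

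Finally, the exposure is slight. As described, the baby has no separate research puncture or line, and harm attributable to the research draw rather than to the clinical one would be rare.

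All of this stands, and it limits the size of the point. It does not repair the rule. The case report form has no stated causality judgement, timeline or review. The local route depends on requirements outside the protocol and inherits the definition in 6.1. Discretion means that sites may classify the same event differently.

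**Conclusion.** The point holds in this form: a serious event that a site attributes to research sampling, but of a kind common in HIE, is not required to be reported as an SAE to the Chief Investigator, Sponsor or Ethics Committee. In addition, the definition in 6.1 and the qualifiers in 6.2 do not fit together. This follows from the rule as stated, not from detail left to another document.

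The size is small. The number of such events cannot be calculated from the protocol and is probably very low, and the scientific results are untouched. The amendment is worthwhile because it is cheap and because the present rule orders the judgements wrongly.

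The conclusion assumes that expectedness is judged by type of event against the disease, as 6.2 is worded, and that the case report form and SAE form add no causality assessment beyond what the protocol describes.

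**What to change.** - **Section 6.1:** remove the words that make unexpectedness part of the SAE definition, so that seriousness, expectedness and relatedness are judged separately.
- **Section 6.2, site step:** have the local investigator judge every serious event in a baby or parent for its relation to study procedures. Any event judged possibly related goes to the Chief Investigator within the existing 24 hours, whether or not it is expected in HIE. The unexpected SAEs already reported continue as now.
- **Section 6.2, Ethics Committee step:** keep the two conditions, but judge expectedness against the study procedures instead of the disease.

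The cost is a wording amendment, a relatedness tick-box on the case report form and SAE form, and a few extra SAE forms. No added procedures or participants are needed.

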7. REGULATORY ISSUES

7.1 REGULATORY & ETHICS APPROVAL

This study has been reviewed and approved by the Health Research Authority and the South West - Exeter Research Ethics Committee. The study will be conducted in accordance with the recommendations for physicians involved in research on human subjects adopted by the 18th World Medical Assembly, Helsinki 1964 and later revisions. The study will also receive confirmation of capacity and capability from each participating NHS Trust before accepting participants into the study.

7.2 CONSENT

Since the study aims to obtain information that will inform early treatment decisions (i.e. within 6 hours of birth), it is essential that the data collection begins as soon as possible after birth, and certainly within 6 hours of birth. Hence the blood collection may begin before informed parental consent is obtained (deferred consenting) at the same time as the clinical blood sample collection on admission.

Parents will be informed about the study at the earliest appropriate opportunity (after being explained about their baby's clinical status and when they feel ready) and will be given the Parent Information Leaflet

Genomic Imaging in Neonatal Encephalopathy

(PIL). Parents wishing to participate in the study will be asked to sign an informed consent form, once ready, and be given a copy for their records (with the PIL). If the parents do not wish to participate in the study, data collection will be interrupted and the blood samples obtained up to that point will be discarded.

Whether or not the parent(s) decide to take part in the study shall not affect the clinical decisions made during the care of the baby, nor the quality of care provided. All participants are free to withdraw from the study at any time without giving any reason and without prejudicing further treatment.

7.3 CONFIDENTIALITY

The Chief Investigator will preserve the confidentiality of participants taking part in the study according to the Data Protection Act, UK. Personal identification data including telephone numbers and all contact details will be stored (i) As hardcopies in a research folder in locked cupboards in the site Principal Investigator's office, and Imperial College London research office (ii) On NHS computers at the recruiting sites (only for babies recruited from that site) (iii) On a secure and encrypted server at Imperial College London.

All personal data will be stored for a period of 10 years, and will be destroyed using standard Imperial College London protocols (including removal by specialist software for electronic data), unless parental consent for further research is obtained at that time.

Gene expression data will be stored without any identifying information, apart from reference study numbers. All MR data is stripped of identifying information upon export from the scanner, and all other records only reference study numbers. Any remaining potentially sensitive data which are necessary to know for the purposes of study (e.g. date of birth) will be kept on a central, backed-up and encrypted drive on the Imperial College London network, which is only accessible from a separate physical location. Access to each of these areas is tightly controlled, and new users requiring access to these data will require formal authorisation from the Chief Investigator.

MR data will be again anonymised using the study number, and encrypted with a password prior to transfer. Imperial College London file transfer protocols will be used for data transfer. All research data will be stored at Imperial College London, for a period of 10 years.

7.4 INDEMNITY

Imperial College London holds insurance policies for both negligent harm and non-negligent harm, which apply to this study.

7.5 SPONSOR

Imperial College London will act as the main Sponsor for this study. Delegated responsibilities will be assigned to the NHS trusts taking part in this study.

7.6 FUNDING

The Medical Research Council, UK and Garfield Weston Foundation funds this study. There are no payments offered to the study participants.

7.7 AUDITS

The study may be subject to inspection and audit by Imperial College London under their remit as sponsor and other regulatory bodies to ensure adherence to both GCP and the NHS Research Governance Framework for Health and Social Care (2nd edition).

8. STUDY MANAGEMENT

The day-to-day management of the study will be co-ordinated through the Centre for Perinatal Neuroscience, Imperial College London. For any queries, please email [contact].

